## **4. Study Population**

### **4.1. Number of Participants**

The study is open to chronic HBV carriers with no recent (3 months) history of any clinically significant conditions, which, in the opinion of the investigator, would jeopardize the safety of the patient or impact the validity of the study results.

Diagnosed CHB is defined by the following values established during screening period:

- HBV virally suppressed with HBV DNA <LLOQ and on stable single NA treatment of at least 12 months duration (ETV or TDF)
- All genotypes, stratified A vs. non-A
- HBeAg negative or positive (expected ratio 7/3): stratification across study arms
- HBsAg plasma levels >100 IU/mL.

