#### 6.2.2.1. Treatment Visit 1 (Week 1 [Day 1])

The treatment Visit 1 is planned on Day 1. Following activities are planned for the visit:

- Confirm patient's eligibility prior to randomization
- Review and record patient's prior and concomitant medications
- Perform drugs of abuse screen pre-dose
- Record patient's body weight
- Calculate BMI
- Perform symptom-directed physical examination
- Perform vital signs (systolic/diastolic BP, heart rate, temperature, respiratory rate) evaluation pre-dose
- Perform AUDIT-C
- Randomization
- Pruritus assessment
- AE monitoring
- Perform clinical laboratory analysis including haematology, serum chemistry panel (including liver safety testing: ALT, AST, Alkaline Phosphatase, Gamma Glutamyl Transferase (GGT), Total Bilirubin and Albumin), coagulation tests and lipid and metabolic profile
- Perform urine pregnancy test (for WOCBP only)
- Perform Dipstick urinalysis for all male and female patients
- Perform 12-Lead ECG
- Sampling for analysis of HBV response markers

---

 For positive HCV antibody-test results only, a PCR-based quantitative HCV viral load assessment will also be performed.

 All subjects must have the blood samples collected at pre-dose for quantitative HBV tests: HBsAg, HBV-DNA, HBV-pgRNA, HBcrAg and HBeAg (the later only for anti-HBe positives subjects).

- PD biomarker sampling
- Liver fibrosis and inflammation assessment
- PK Sampling
- Dispense patient diary and explain use
- Dispense EYP001a or placebo and NA (choice between ETV or TFV is at the Investigator discretion)

6.2.2.2. *Treatment Visit 2 (Week 2 [Day 14 ± 3 days])*

The treatment Visit 2 is planned on Day 14 ± 3 days in Week 2. Following activities are planned for the visit:

- Review and record patient's prior and concomitant medications
- Perform vital signs (systolic/diastolic BP, heart rate, temperature, respiratory rate) evaluation pre-dose
- Pruritus assessment
- AE monitoring
- Perform clinical laboratory analysis only liver safety testing: ALT, AST, ALP, GGT, total bilirubin, thrombocytes and albumin
- Sampling for analysis of HBV response markers
- PD biomarker sampling
- PK Sampling
- Review returned patient diary and dispense new diary
- Collect used/unused study drug and assess compliance

6.2.2.3. *Treatment Visit 3 (Week 4 [Day 28 ± 3 days])*

The treatment Visit 3 is planned on Day 28 ± 3 days in Week 4. Following activities are planned for the visit:

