### **11.3.2. Demographic and Baseline Characteristics**

Demographic and baseline information including treatment history, HBV genotype, age, gender, BMI, weight, and height will be summarised by treatment group using the ITT set.

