2.5 Randomization

Sequential screening numbers will be assigned to patients at the time of informed consent signing. As they are enrolled into the study and after eligibility on Day -3 at the earliest and prior to dosing on Day 1 at the latest, patients will be assigned to a unique randomization number which are randomly assigned to treatment according to the specified randomization scheme.

The randomization schedule will be computer-generated before the start of the study.

An Interactive Web Response System (IWRS) will be employed to manage patient and treatment assignments.

Patients will be randomized prior to study drug (EYP001a or placebo and NA) administration on Day 1 in the ratio of approximately 3:1 (37:12) into 2 arms:

- Experimental Arm: EYP001a 200 mg QD + NA daily (37 patients)
- Control Arm: Placebo + NA daily (12 patients)

The ratio will be controlled through block randomization.

Patients will also be stratified per HBeAg status, based on medical history HBeAg value or established during screening, to obtain a balanced randomization to both study arms.

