13.1 Adverse Events

All AEs including will be coded using MedDRA. All AE summaries will be restricted to TEAEs only. Summary tables will include the number of participants (%) experiencing an event and the number of events. Participants will be counted only once for each SOC and PT level (categorical descriptive analysis).

AE and SAE will be analysed taking into account any identified subject with Sars-Cov2 infection during and post-pandemic measures phases. Such an analysis will be operated through the independent Data Monitoring Committee (DMC).

The TEAE summaries will include:

- Overall summary of TEAEs.
 - Number of TEAEs
 - Number of TEAEs with Severity \geq Grade 3 Severe
 - Number of Serious TEAEs
 - Number of Study Drug Related TEAEs (Drug Related: A Possibly, Probably or Definitely related TEAE)
 - Number of Entecavir (ETV) Related TEAEs (Drug Related: A Possibly, Probably or Definitely related TEAE)
 - Number of Tenofovir Disoproxil Fumarate (TDF) Related TEAEs (Drug Related: A Possibly, Probably or Definitely related TEAE)
 - Number of TEAEs leading to study drug withdrawal
- TEAE summary by SOC and PT.
- TEAE summary of serious events by SOC and PT.
- TEAE summary by SOC, PT and Severity.
- TEAE summary by SOC, PT and relationship to study drug.
- TEAE summary by SOC, PT and relationship to ETV.
- TEAE summary by SOC, PT and relationship to TD.
- TEAE summary of events leading to the study drug discontinuation by SOC and PT.

All AEs will be listed and will include verbatim term, PT, SOC, treatment, causality to study drug, ETV and TDF, severity, seriousness, outcome, and action taken with regards to the study drug and AE. Separate listings will be created for SAEs and events leading to study drug withdrawal.

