Percentages are calculated (the denominator used for the calculation) based on the number of participants in the safety set in each treatment group (N).

World Health Organization-Drug Dictionary (WHO-DD) Version xx, YYYY

Table 14.3.3.1 Summary of Overall Treatment Emergent Adverse Events (*Safety Set*)

	Group 1 (N=xx) n (%) m	etc.	Group x (N=xx) n (%) m
Number of Participants Reporting at least:			
One TEAE	xx (xx.x%) xx	xx (xx.x%) xx	xx (xx.x%) xx
One Serious TEAE	xx (xx.x%) xx	xx (xx.x%) xx	xx (xx.x%) xx
One TEAE with Common Terminology Criteria for Adverse Events (CTCAE) Toxicity ≥ Grade 3	xx (xx.x%) xx	xx (xx.x%) xx	xx (xx.x%) xx
One Study Drug Related TEAE	xx (xx.x%) xx	xx (xx.x%) xx	xx (xx.x%) xx
One Entecavir (ETV) Related TEAE	xx (xx.x%) xx	xx (xx.x%) xx	xx (xx.x%) xx
One Tenofovir Disoproxil Fumarate (TDF) Related TEAE	xx (xx.x%) xx	xx (xx.x%) xx	xx (xx.x%) xx
One TEAE Leading to Discontinuation of Study Drug	xx (xx.x%) xx	xx (xx.x%) xx	xx (xx.x%) xx

Source: Listing 16.2.7.1

Treatment Emergent Adverse Events (TEAEs) are defined as adverse events that occurred following the first administration of study medication. If a participant has multiple occurrences of a TEAE, the participant is presented only once in the Participant count (n) column for a given System Organ Class and Preferred Term. Occurrences are counted each time in the mentions/Occurrence (m) column.

Treatment Related TEAE is defined as any TEAE reported as being "Possibly", "Probably" or "Definitely" to Study Drug/EV/TDF.

Percentages are calculated (the denominator used for the calculation) based on the number of participants in the safety set in each treatment group (N).

Medical Dictionary for Regulatory Activities (MedDRA) Version xx.x

Table 14.3.3.2 Summary of Treatment Emergent Adverse Events by System Organ Class and Preferred Term (Safety Set)

	Group 1 (N=xx)		etc.	Group x (N=xx)	
	n (%)	m		n (%)	m
Participants with at least one TEAE	xx (xx.x%)	xx	xx (xx.x%)	xx	xx (xx.x%)
SOC1	xx (xx.x%)	xx	xx (xx.x%)	xx	xx (xx.x%)
PT1	xx (xx.x%)	xx	xx (xx.x%)	xx	xx (xx.x%)
....					
SOC2	xx (xx.x%)	xx	xx (xx.x%)	xx	xx (xx.x%)
PT1	xx (xx.x%)	xx	xx (xx.x%)	xx	xx (xx.x%)
PT2	xx (xx.x%)	xx	xx (xx.x%)	xx	xx (xx.x%)
PT3	xx (xx.x%)	xx	xx (xx.x%)	xx	xx (xx.x%)
PT4	xx (xx.x%)	xx	xx (xx.x%)	xx	xx (xx.x%)
....					

Source: Listing 16.2.7.1

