Unrelated	xx (xx.x%) xx	xx (xx.x%) xx	xx (xx.x%) xx
....			

Source: Listing 16.2.7.1

Treatment Emergent Adverse Events (TEAEs) are defined as adverse events that occurred following the first administration of study medication. If a participant has multiple occurrences of a TEAE, the participant is presented only once in the Participant count (n) column for a given System Organ Class and Preferred Term. Occurrences are counted each time in the mentions/Occurrence (m) column.

Percentages are calculated (the denominator used for the calculation) based on the number of participants in the safety set in each treatment group (N).

Medical Dictionary for Regulatory Activities (MedDRA) Version xx.x

Table 14.3.3.4.3 Summary of Treatment Emergent Adverse Events by Relationship to TD by System Organ Class, Preferred Term (Safety Set)

	Group 1 (N=xx) n (%) m	etc.	Group x (N=xx) n (%) m
Participants with at least one TEAE related to TD	xx (xx.x%) xx	xx (xx.x%) xx	xx (xx.x%) xx
Definitely Related	xx (xx.x%) xx	xx (xx.x%) xx	xx (xx.x%) xx
Probably Related	xx (xx.x%) xx	xx (xx.x%) xx	xx (xx.x%) xx
Possibly Related	xx (xx.x%) xx	xx (xx.x%) xx	xx (xx.x%) xx
Unlikely Related	xx (xx.x%) xx	xx (xx.x%) xx	xx (xx.x%) xx
Unrelated	xx (xx.x%) xx	xx (xx.x%) xx	xx (xx.x%) xx
SOC1	xx (xx.x%) xx	xx (xx.x%) xx	xx (xx.x%) xx
Definitely Related	xx (xx.x%) xx	xx (xx.x%) xx	xx (xx.x%) xx
Probably Related	xx (xx.x%) xx	xx (xx.x%) xx	xx (xx.x%) xx
Possibly Related	xx (xx.x%) xx	xx (xx.x%) xx	xx (xx.x%) xx
Unlikely Related	xx (xx.x%) xx	xx (xx.x%) xx	xx (xx.x%) xx
Unrelated	xx (xx.x%) xx	xx (xx.x%) xx	xx (xx.x%) xx
PT1	xx (xx.x%) xx	xx (xx.x%) xx	xx (xx.x%) xx
Definitely Related	xx (xx.x%) xx	xx (xx.x%) xx	xx (xx.x%) xx
Probably Related	xx (xx.x%) xx	xx (xx.x%) xx	xx (xx.x%) xx
Possibly Related	xx (xx.x%) xx	xx (xx.x%) xx	xx (xx.x%) xx
Unlikely Related	xx (xx.x%) xx	xx (xx.x%) xx	xx (xx.x%) xx
Unrelated	xx (xx.x%) xx	xx (xx.x%) xx	xx (xx.x%) xx
....			

Source: Listing 16.2.7.1

Treatment Emergent Adverse Events (TEAEs) are defined as adverse events that occurred following the first administration of study medication. If a participant has multiple occurrences of a TEAE, the participant is presented only once in the Participant count (n) column for a given System Organ Class and Preferred Term. Occurrences are counted each time in the mentions/Occurrence (m) column.

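### ETV-related and TDF-related TEAE percentages are divided by the whole column although each patient is planned to take only one NA, so they are diluted by NA share wherever both NAs are used (minor)

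*SAP*

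**What the plan says.** SAP 13.1 plans an overall TEAE summary that includes "Number of Entecavir (ETV) Related TEAEs (Drug Related: A Possibly, Probably or Definitely related TEAE"), with the same item for TDF, and then two tables by SOC, PT and relationship to each NA. In the mock tables these are:

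- Table 14.3.3.1, with a row labelled "One Entecavir (ETV) Related TEAE" and a matching TDF row;
- Table 14.3.3.4.2 (relationship to ETV);
- Table 14.3.3.4.3 (relationship to TD).

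All three carry the footnote "Percentages are calculated (the denominator used for the calculation) based on the number of participants in the safety set in each treatment group (N"). SAP 3.1 has a general denominator rule based on non-missing data, but it gives way where a specific rule is stated, and this footnote is such a rule.

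On who takes what, protocol 4.1 describes patients "on stable single NA treatment of at least 12 months duration (ETV or TDF"). Protocol 6.2.2.1 has the site "Dispense EYP001a or placebo and NA (choice between ETV or TFV is at the Investigator discretion"). SAP 2.5 says "Patients will also be stratified per HBeAg status, based on medical history HBeAg value or established during screening" and names no NA factor. Table columns are arm by HBeAg status (SAP 3.7), never by NA.

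Protocol 11.3.2 plans a by-arm summary of "Demographic and baseline information including treatment history, HBV genotype, age, gender" and other items. SAP 7.1 and Table 14.1.2 contain no NA variable. The NA taken does appear in Listings 16.2.5.2 and 16.2.5.3.

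**The concern.** A patient who never takes ETV is not at risk of an ETV-related event, yet counts in the ETV denominator; the same holds for TDF. Two things follow in any column where both NAs are used. Each percentage is lower than the rate among the patients exposed to that drug. And a difference between arms can arise from who was on which NA, with no difference in risk.

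A secondary objective is the safety of EYP001a in combination with NA. These are the planned tables that attribute events to the background drug, so a reader may look here for a sign that EYP001a alters its tolerability. An uneven NA mix could create such a sign or hide one.

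The SAP restricts denominators to the relevant subset elsewhere: females for childbearing potential (Table 14.1.2) and anti-HCV positives for HCV viral load (Table 14.1.3).

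**Working it through.** The documents state no rate, NA split or precision for these tables, so there is no planned figure to reproduce. Arm sizes are from SAP 2.5: "Experimental Arm: EYP001a 200 mg QD + NA daily (37 patients"), and 12 on placebo. The NA splits and event rates below are assumptions.

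**1. Dilution.** Let N be the safety-set size of a column, s the share on ETV and r the rate of ETV-related TEAEs among ETV users.

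Printed rate = (r × s × N) / N = r × s.

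The TDF rate is multiplied by (1 − s) in the same way. With r = 20% for both drugs:

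| ETV share s | ETV printed | TDF printed |
|---|---|---|
| 25% | 5% | 15% |
| 50% | 10% | 10% |
| 75% | 15% | 5% |
| 100% | 20% | no users |

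The last row marks the limit of the point: where a whole column takes one NA, that NA's rate is correct.

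**2. Effect on an arm contrast, in whole patients (assumed).** Suppose 24 of 37 EYP001a patients take ETV, 6 of them with an ETV-related TEAE, and 4 of 12 placebo patients take ETV, 1 of them with such an event.

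- Among users: 6/24 = 25.0% and 1/4 = 25.0%.
- As the footnote prints it: 6/37 = 16.2% and 1/12 = 8.3%.

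The ETV shares here are 64.9% and 33.3%, a gap of about 32 points, chosen to show the mechanism.

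**3. How likely a gap in NA mix is.** With K of M patients on ETV and NA type unrelated to allocation, the number x on ETV in the active arm is hypergeometric. Sum P(x) over all x with |x/n₁ − (K − x)/n₂| ≥ 0.20.

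For M = 49, n₁ = 37, n₂ = 12, K = 24, the condition is met at x ≤ 16 or x ≥ 20:

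- lower tail 0.0007 + 0.0064 + 0.0326 + 0.1008 = 0.1405;
- upper tail 0.1246 + 0.0448 + 0.0098 + 0.0012 + 0.0001 = 0.1805;
- total 0.321.

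The result is not smooth in K, because shares of 12 move in steps of 8.3 points:

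| On ETV, of 49 | 9 | 12 | 14 | 15 | 16 | 22 | 24 |
|---|---|---|---|---|---|---|---|
| P(gap ≥ 20 points) | 0.09 | 0.25 | 0.14 | 0.15 | 0.29 | 0.18 | 0.32 |

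The values mirror above 24 (K and 49 − K agree). Over K = 9 to 40 the range is 0.09 to 0.32. A gap of 30 points or more has probability 0.095 at K = 24.

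**4. At the size reached.** SAP 15 records suspension of enrolment after about 25 randomizations. At 3:1 that is about 25 × 37/49 = 18.9, so 19:6 is assumed. The same sum gives 0.38 at 12 of 25 on ETV and 0.28 at 6 of 25. For 5 to 20 of 25 on ETV it lies between 0.28 and 0.38, except at 8 and 17, where it reaches 0.62.

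**The case against.** The strongest reply is that the footnote declares its denominator. The printed figure is then a correct statement of the share of the arm with an event judged ETV-related, and it is understated only when read as risk among ETV takers. Cells show counts as well as percentages, safety carries no hypothesis test, and Tables 14.3.3.4.2 and 14.3.3.4.3 go to neither DSMC package. All of that stands and lowers the severity. It does not make the whole column the right base for comparing arms. Table 14.3.3.1, with its two affected rows, goes to both DSMC meetings.

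An NA-specific denominator also has a cost. At an HBeAg-negative to positive ratio of 7:3 (protocol 4.1), six placebo patients would include about 6 × 0.3 = 1.8 HBeAg positives, so some cells would have a base of 0 to 2. Changing the denominator alone would also be faulty. The shells have rows for unlikely and unrelated events. If a TDF patient's events are recorded as unrelated to ETV, they enter the ETV table's numerator, and a percentage could pass 100%. Both objections are sound and shape the fix.

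A reader might go further than the documents allow in four ways:

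- **A 1.8-fold spurious difference.** A 20% user rate with 60% versus 4/12 on ETV gives 0.20 × 0.60 = 12.0% against 0.20 × 4/12 = 6.7%. The second figure is 0.8 of a patient. With N = 12 the table prints 0% or 8.3%, so this is a difference in expectation only.
- **The protocol already requires NA variables at baseline.** Section 11.3.2 names treatment history without defining it.
- **No summary could show the NA split.** The concomitant-medication table excludes study drug. SAP 2.1 counts NA as study drug, but SAP 13.1 separates them. Whether NA would appear there is unclear.
- **NA is simply a site choice.** Section 6.2.2.1 gives discretion, but patients enter after at least 12 months of stable NA treatment, so most of the mix may come from prior care. Either way it is not balanced by design.

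**Conclusion.** Wrong as written, low severity. The denominator follows from the footnotes and needs no assumption. Dilution arises in every column where both NAs are used and equals the share on that NA. The chance of a 20-point or larger gap in ETV share is about 9% to 32% at 37:12, and about 28% to 38% at most splits at 19:6. These figures assume the NA split, allocation unrelated to NA type and, for the second range, the 19:6 arm sizes. The documents do not show that such a gap occurred, nor that any safety conclusion was affected. The tables are descriptive, and the counts would be right under either rule.

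**What to change.** - In Tables 14.3.3.4.2 and 14.3.3.4.3 and the ETV and TDF rows of Table 14.3.3.1, restrict both numerator and denominator to safety-set patients in the column who received that NA. Print that n in the column header or beside the row.
- Show counts without percentages where that n is very small or zero, which is likely in the placebo HBeAg columns. Set the threshold in the SAP.
- Count a patient whose NA changes on study under each NA taken. Protocol 4.6 allows for NA to be modified after a confirmed breakthrough.
- Add NA at Day 1 (ETV or TDF) by arm to Table 14.1.2. This is consistent with treatment history in protocol 11.3.2, though not spelled out there.

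The cost is a SAP shell and programming edit. The NA taken is already in Listings 16.2.5.2 and 16.2.5.3, so no new data are needed.
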